**Protocol 01**

**06/16/2014**

## A. STUDY AIMS

Specific Aim 1: To determine if routine dietary supplementation with enteral tube feeding affects recovery and quality of life after esophagectomy. Medicare rules only pay for enteral supplements (tube feeding) if the patient needs alternative feeding for greater than 3 months. Many insurers have adopted these rules, without evidence in post-operative patients.

- We hypothesize that routine post-operative supplementation will enhance patients recovery and quality of life, by increasing the time of adequate nutrition.

Specific Aim 2: To determine the occurrence of common complications and readmissions post-operatively between patients who are routinely discharged with tube feeding and those that are not. If patients are not discharged with tube feeds, they must obtain all of their nutrition by mouth, which may be difficult in the early post-operative period.

- We hypothesize that routine use of tube feeding may reduce the occurrence of complications.

The secondary aims of this randomized clinical trial are:

- To compare costs of care between groups.
- To assess how length of stay (LOS) and readmission rates are affected by routine use of tube feeding, as well as costs of care.
- Rates of occurrence of tube feeding or jejunal tube-specific complications

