### **D. OUTCOME MEASURES**

The primary outcome measure for specific aim 1 will be the quality of life and patient satisfaction as measured by post-operative survey instruments.

Secondary Outcomes for specific aim 1:

- Complications following surgery (jejunal tube)
- Length of stay
- Costs

The primary outcome for specific aim 2 will be the occurrence of post-operative complications such as: atrial fibrillation, delirium, anastomotic leak, pneumonia within the 30-day post-operative time frame.

Secondary Outcomes for specific aim 2:

- Readmission rates and costs of care.

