#### **b. Specific Aim 2**

Occurrence and severity of complications will be recorded by HUM00012731. Patients will be assessed at discharge and return visits. Adverse events following surgery (e.g, pneumonia, DVT, PE, anastomotic leak, atrial fibrillation, delirium, etc.) will be identified prospectively by the study team

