**J. STATISTICAL AND DATA MANAGEMENT CONSIDERATIONS**

**For the specific aims:**

Specific Aim 1: Quality of Life measurements will be compared at 6 months, using descriptive statistics.

Specific Aim 2: Calories will be compared between groups.

**For the secondary aims:** Height and weight will be compared between groups at 30 days and 6 months.

**Sample size justification:** This was measured with the possible recruitment pool and differences between groups.

**Interim analysis:** At 50% recruitment or three years.

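### Section J analyses Specific Aim 2 by calories, although the aim's hypothesis, primary outcome and measurements are all complications

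*Combined protocol and SAP*

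**What the plan says.** Section A sets Aim 2 as determining "the occurrence of common complications and readmissions post-operatively between patients who are routinely discharged with tube feeding and those that are not", with the hypothesis "We hypothesize that routine use of tube feeding may reduce the occurrence of complications". Section D defines the aim's primary outcome as "the occurrence of post-operative complications such as: atrial fibrillation, delirium, anastomotic leak, pneumonia within the 30-day post-operative time frame". Section H takes the Aim 2 instruments from the companion study, and H.1.b states "Occurrence and severity of complications will be recorded by HUM00012731" and "Patients will be assessed at discharge and return visits". Table 1 in Section N assigns its adverse-event row to Aim 2.

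Section J is the only section that sets out analyses. Its entire entry for this aim is "Specific Aim 2: Calories will be compared between groups". It gives no time point, effect measure or method. For the secondary aims it names height and weight at 30 days and 6 months.

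**The concern.** The analysis section and the rest of the plan name different variables for the same aim. This goes beyond missing detail: Section J makes a definite statement, and the variable it names is not the one the aim is about. An analyst who followed it would report calories, would have no described source for them, and would not have tested whether tube feeding reduces complications. If the error were noticed only at analysis, the event list, window and effect measure for complications would be chosen with outcomes already available. Section J also plans an interim look at half recruitment or three years, so that could happen before the trial ends.

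**Working it through.** There is no figure to reproduce. Section J gives no effect size, error rate, power or event rate, and the sample size in Section K is an unfilled placeholder. The check is a comparison of sections, followed by simple counts.

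**1. Which variable defines Aim 2**

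| Place | Variable |
|---|---|
| Section A, aim | Complications and readmissions |
| Section A, hypothesis | Complications |
| Section D, primary outcome | Complications, 30 days from surgery |
| Section H, Aim 2 instruments | Complications assessment |
| H.1.b, measurement | Occurrence and severity of complications |
| Table 1, row assigned to Aim 2 only | Adverse events |
| **Section J, analysis** | **Calories** |

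All six other places concern complications, and none mentions calories.

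**2. Where calories could come from**

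- Section D: not an outcome.
- Section H: not a measure.
- Section I: not among the history or examination items.
- Table 1: 0 of 9 rows (eligibility, consent, demographics, comorbidity index, quality of life, randomisation, adverse events, length of stay, costs).
- Section F mentions caloric needs, but only to describe the intervention.
- Section B says that what patients eat is poorly documented both before and after they go home, so routine records cannot be assumed to fill the gap.
- The companion study's forms are not fully described. If they record intake, the plan does not say so.

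**3. Counts**

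- Section D lists seven outcomes: quality of life, satisfaction, complications, jejunal-tube complications, length of stay, readmission and costs. Section J covers 1 of 7 (quality of life), or 1 of 6 if quality of life and satisfaction are merged.
- Section J compares four variables: quality of life, calories, height and weight. Of these, 4 − 1 = 3 are not Section D outcomes.
- Of the four listed secondary outcomes (jejunal-tube complications, length of stay, readmission, costs), 0 of 4 have a line in Section J.

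**4. Height and weight**

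Both are examination items in Section I.1, and the Demographics row of Table 1 may cover baseline values. No follow-up measurement is scheduled. Assuming discharge on POD 8, the clinic visit at 2 weeks with a one-week window falls between POD 8 + 14 − 7 = 15 and POD 8 + 14 + 7 = 29. Section I's 2 to 3 weeks, if counted from discharge, extends this to POD 8 + 21 + 7 = 36. A weight near day 30 is therefore possible, though not planned. The 6-month contact is remote, and no method of weighing is given.

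**5. Randomisation inside the 30-day window**

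Under Section F, assignment takes place at POD 8 or before discharge. From POD 8, 30 − 8 = 22 days remain (22/30 = 73%). From POD 14 (an assumption), 30 − 14 = 16 days remain (16/30 = 53%). These are shares of the calendar. The documents do not say how events are spread over the window, so they measure neither lost events nor bias. They show only that part of the Section D window comes before assignment, and events in that part cannot be effects of assignment.

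**The case against.** The strongest reply is that Section J is silent on complications and does not rule them out. Section A plainly intends a between-group comparison of complications and readmissions, and lists "To compare costs of care between groups" among the secondary aims. That stands as evidence of intent. It supplies no method, however, and it does not explain why the one Aim 2 analysis names another variable. A reader might infer that the plan abandons the complications comparison; the documents do not support that.

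It can also be said that this is a working draft with visible placeholders. That is true of the sample size and the randomisation text, but the calories line is a finished sentence.

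Four further inferences go too far:

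- **That the event lists conflict.** Section D names four events, and H.1.b names six ("pneumonia, DVT, PE, anastomotic leak, atrial fibrillation, delirium, etc"), adding DVT and PE. Both lists are introduced as examples, so they do not contradict each other. What stands is that the list is open.
- **That 30 days applies throughout.** Only Section D gives that window for complications. Section H also refers to long-term data, and Table 1 collects adverse events to 6 months. Wider collection is compatible with a 30-day outcome, but the analysis must say which events count.
- **That no Aim 2 sample size can be set.** It could already be based on the Section D outcome. The unfilled number is a separate defect.
- **That the mismatch requires a new primary outcome.** It does not. Making post-randomisation events primary would be an amendment of Section D and should be proposed as one.

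**Conclusion.** The point holds and needs correcting before any outcome comparison. As written, Section J gives the Aim 2 primary outcome no analysis and replaces it with a variable that the plan does not say how to collect. The conclusion rests on the text alone and depends on no assumed number. It takes Section J as the complete statement of analyses. If the companion study's forms do record intake, calories would gain a source, but the mismatch with the hypothesis and primary outcome would remain.

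The secondary line is a lesser matter. A reader might class the four unanalysed secondary outcomes with the Aim 2 error, but for those outcomes the fault is mostly missing detail. Height and weight are at least data items in Section I, and the gap there is unscheduled follow-up. The effect on power or precision cannot be stated, because the documents give neither a sample size nor a complication rate.

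**What to change.** **Main change.** Replace the Aim 2 line in Section J with a comparison, by original assignment, of the proportion of randomised patients with at least one complication from a fixed list within 30 days of surgery, reported as a risk difference with a 95% CI. Summarise severity by group, since H.1.b records it. Settle one event list, covering the examples in Section D and H.1.b, before any comparison is made. State how this analysis set fits with Section C, which leaves patients who are tube-feeding dependent at discharge out of the analysis: a patient randomised on POD 8 could later fall under that rule.

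**Timing.** Report events with onset before and after randomisation separately. If the sponsor prefers post-randomisation events as primary, say openly that this amends Section D.

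**Calories.** Keep them only as exploratory, and only if Table 1 gains a collection method and time point.

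**Lower priority.** Add comparisons of jejunal-tube complications, readmission, length of stay and costs. Count length of stay and costs from randomisation, or acknowledge the stay that precedes it. Schedule follow-up weight if it is to be compared.

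**Cost.** Rewording Section J and Table 1 is cheap. Onset dates are needed, and a field must be added if the companion study's forms lack one. Counting from randomisation gives fewer events than counting from surgery. Precision stays unknown until the sample size and an expected complication rate are stated.

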## B. BACKGROUND AND SIGNIFICANCE

Nutritional support is taking on an increasing focus in peri-operative surgical care. It is particularly important in esophageal resection, which is a high-risk operation in a patient population whose pre-operative condition may be reduced due to pre-operative chemo- and radio-therapy, as well as dysphagia from the cancer. Post-operatively, patients are routinely cleared to take nutrition by mouth once an esophagram is done post-operative day 7 and shows no abnormality.

Tube feeding should be at goal by day 7, but is discontinued once patients are discharged, as long as they are able to eat, i.e., do not have evidence of anastomotic leak or other serious complications. The amount patients are able to eat is frequently variable, and is not well recorded prior to or after discharge. There may be a dip in calories consumed, which if severe, will lead to readmission for

hydration, failure to thrive, or possibly the development of a post-operative complication.

Currently all patients are discharged with the jejunal feeding tube placed at the operation, just in case they are unable to eat post-operatively due to an unforeseen complication. Since many insurers and Medicare require patients to pay for tube feeding needed for less than three months (~\$800/month and up, plus the services of a home health nurse), we do not routinely require patients use the feeding tube once discharged.

For esophagectomy specifically, and upper gastro-intestinal surgery in general, there is very limited literature looking at this question. Small randomized studies have not shown a benefit to routine tube feeding, although the numbers were very small, ranging from 12 to 70 in each group. Furthermore, the duration of tube feeding averaged 14 days, and even in the groups being fed enterally, were not meeting caloric needs in the period studied.

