## **F. RANDOMIZATION AND MASKING**

Randomization envelopes will be created at the start of the study. Each envelope will be opened prior to discharge or at POD#8 if patients are able to take adequate nutrition by mouth, to determine if post-operative tube feeding will be continued or not.

By consenting to the study, patients agree to continue tube feeding for at least 50% of caloric needs for 1 month post-operatively. Cross-over after randomization will be permitted for patient condition, although once randomized, patients will be analyzed by the original group.

- A copy of the signed research consent form must be included in the patient's hospital chart.

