## **H.3 Schedule of Measurements**

Section N details the schedule of measurements. Data will be collected preoperatively at the initial screening visit, during the perioperative period, at the follow-up appointment (2 weeks following discharge), and at 1 month, 3 months, and 6 months (by telephone or mail).

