## **I. DATA COLLECTION**

All data collection following surgery will be performed by research staff other than the study surgeon. This will reduce bias by maintaining masking in data collection of outcome measures. All research staff will be trained and certified to perform data collection procedures. Allowable windows for timed evaluations are specified in Section N and include a one-week window on each side of the postoperative visit planned at 2-3 weeks. The assessments at 1-month, 3-months, and 6-months will take place by mail and will not require a visit to the clinical site.

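### Section J compares calories and follow-up weight, but the protocol names no calorie source and Table 1 schedules no intake, tube-feeding status or follow-up weight

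*Combined protocol and SAP*

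**What the plan says.** Section J plans two nutritional comparisons. For Aim 2 the entire entry is "Specific Aim 2: Calories will be compared between groups". For the secondary aims it is "Height and weight will be compared between groups at 30 days and 6 months". The two time points belong to height and weight; calories have none.

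The assigned treatment is itself defined in calories. Under Section F, "patients agree to continue tube feeding for at least 50% of caloric needs for 1 month post-operatively". Cross-over for patient condition is allowed, and Section L expects that some control patients may need to restart feeding.

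H.3 refers to Section N for the schedule and places data collection after discharge "at the follow-up appointment (2 weeks following discharge), and at 1 month, 3 months, and 6 months (by telephone or mail"). Section I gives mail as the mode for the last three. Weight is listed in I.1.b, under physical examination, without a time point.

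Section H takes baseline, quality-of-life and complications data from HUM00012731. For patients who decline co-enrolment it names only the QLQ-C30 and the demographics and history forms, and the latter are given once, before surgery.

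**The concern.** Aim 1 expects tube feeding to help "by increasing the time of adequate nutrition". Section B criticises earlier trials because patients, "even in the groups being fed enterally, were not meeting caloric needs in the period studied". It also says of current practice: "The amount patients are able to eat is frequently variable, and is not well recorded prior to or after discharge". Intake is therefore the link between the treatment and its hoped-for effect, and it is known to be poorly documented in routine care.

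If intake and tube-feeding status are not recorded, a finding of no difference in quality of life or complications has two explanations that the trial could not separate. Either the extra nutrition was delivered and did not help, or the arms ended with similar intake because feeding stopped early in one arm or restarted in the other. This trial would then share the weakness it sees in its predecessors. Intake that is not recorded at the time cannot be reconstructed later, so the gap has to be closed before enrolment.

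**Working it through.** The protocol gives no figure to reproduce here: no sample size, power or effect size is stated. The check sets each Section J variable against the places where it could be collected.

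**Table 1 rows.** Eligibility, Consent, Demographics, Charlson Comorbidity Index, Quality of Life Assessment, Randomization, Adverse Events, Hospital LOS, Costs = 9.
- Rows for calories or intake: 0 of 9.
- Rows for tube-feeding status: 0 of 9.
- Rows for follow-up weight: 0 of 9. Because I.1 groups demographics with physical examination, the Demographics row could include weight, but it is marked at screening only.

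**Calories.** Sections D, H and I name no diet record, feed log or other calorie instrument. Scheduled time points: 0.

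**Contacts after discharge.** Clinic, 1 month, 3 months, 6 months = 4, of which 3 are remote. Only the clinic visit allows a scale weight.

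**Can the clinic visit supply the 30-day weight?** H.3 and Table 1 put it at 2 weeks after discharge. Section I says the allowed windows "include a one-week window on each side of the postoperative visit planned at 2-3 weeks". The discharge days below are assumptions.
- Discharge on POD 8, visit at 2-3 weeks: 8 + 14 = 22 to 8 + 21 = 29; with 7 days either side, POD 15-36.
- Discharge on POD 8, visit at 2 weeks: POD 22; with 7 days either side, POD 15-29.
- Discharge on POD 12, visit at 2-3 weeks with the window: 12 + 7 = 19 to 12 + 28 = 40.

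A weight near POD 30 is therefore possible, but nothing schedules it.

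**Can it supply the 6-month weight?** The latest visit is 28 days after discharge. Take 6 months as about POD 183, counted from surgery (an assumption, since H.3 states no anchor).
- Discharge on POD 8: 183 - 36 = 147 days short.
- Discharge on POD 12: 183 - 40 = 143 days short.
- Discharge on POD 20: 183 - 48 = 135 days short.
- To reach POD 183, discharge would have to be on about POD 183 - 28 = 155.

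So it cannot. A 6-month weight would have to be self-reported at a remote contact, and no item asks for it, or come from HUM00012731.

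**Delivery of the dose.** Checking the dose needs calories by tube (numerator), the patient's caloric need (denominator), and the dates on which feeding stopped or restarted. None of the three is scheduled.

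**The case against.** The strongest reply is that the calorie line is a drafting slip. Calories and weight are not outcomes in Sections A, D or H, whereas Section D makes 30-day complications the Aim 2 primary outcome and Section J never analyses them. Comparing adult height at 30 days and 6 months also suggests rough wording. This stands, and the fix must address the mismatch between Sections D and J. It does not remove the gap: deleting the calorie line would still leave delivery of a calorie-defined treatment unverified.

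A second reply is that other sources may fill in. HUM00012731 may hold weights or intake, and billing data or feeding paid for by the department (Section O) may show some restarted feeding. That is possible, but the protocol names none of these as the source for calories, weight or restart dates. Weights held only in the companion study would also limit the comparison to co-enrolled patients.

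A third is that the document is visibly unfinished, with open queries in the randomization text and in Sections K and L. Those gaps are flagged for completion; this one is not.

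A reader might go further and infer that weight is not collected at all. The documents do not support that: I.1.b lists it, a screening weight is plausible, and the companion forms cannot be seen.

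**Conclusion.** The point holds. Followed as written, the plan has no data source for the calorie comparison and none for 6-month weight in patients who are not co-enrolled. It also cannot describe delivery of the feeding dose or the extent of cross-over. In size: 0 of 9 schedule rows for intake, tube-feeding status or follow-up weight, 0 calorie time points, and 3 of 4 contacts after discharge remote. That the clinic visit cannot supply the 6-month weight does not depend on the assumed discharge days; the exact number of days short does.

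The harm is mainly to the interpretation of a null result. A reader might infer that the gap in itself invalidates the quality-of-life and complications comparisons. It does not, because neither uses calories or weight. Nor should this point be read as endorsing those comparisons. Section C drops patients who are tube-feeding dependent at discharge from analysis, and Section K replaces patients who drop out or are lost; both need separate examination.

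The change should be made before enrolment, but it ranks below settling the primary analyses.

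**What to change.** For all randomized patients in both arms, whether or not co-enrolled, at existing contacts and with identical instructions:

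1. Add a weight row to Table 1: scale weight at screening, randomization and the clinic visit, and self-reported weight at 1 and 6 months.
2. Record each patient's estimated caloric need at randomization. Add a row for a short record of oral plus tube intake at the clinic visit and at 1 month, with the 1-month form handed out at the clinic visit. Where that visit falls late in its window, mail the form ahead. State these time points for calories in Section J.
3. Record the dates of early stopping and of resumption of tube feeding, and report both by original group.
4. Make 30-day complications, as in Section D, the Aim 2 primary analysis in Section J, with calories as a supporting measure of treatment delivery.

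The cost is two schedule rows, one value at randomization, a short form and dated questions, with no new visits. Patients carry some burden, and staff need time to convert records to calories. Some records will be incomplete. Home weights are less precise than clinic weights, and self-report is unblinded, so errors could differ by arm.

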### **E.2. Exclusion Criteria**

- E.2.1 Emergent procedure.
- E.2.2 Less than 18 years of age.
- E.2.3 Inability to provide informed consent or to complete testing or data collection.
- E.2.4 Unwillingness to be randomized.
- E.2.5 Tube feeding dependent on discharge.

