## N. TIMELINE OF VISITS, MEASURES AND FORMS:

Table 1 Timeline of Visits and Data Collection

	Screening & Enrollment	Inpatient (post-op)	Follow-up (Clinic- 2 weeks)	1 Month	3 Months	6 Months	Specific Aim (1 or 2)
Eligibility	X	X*					1/2

Consent	X						1/2
Demographics	X						1/2
Charlson Comorbidity Index	X						1/2
Quality of Life Assessment	X		X	X	X	X	1
Randomization		X					
Adverse Events			X	X	X	X	2
Hospital LOS			X				1/2
Costs						X	1/2

\*assess for continued study eligibility prior to randomization

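### The weight comparison planned for 30 days and 6 months has no specified data source, and height is uninformative as an outcome in adults

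*Combined protocol and SAP*

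**What the plan says.** Section J, under the secondary aims, gives one sentence of analysis: "Height and weight will be compared between groups at 30 days and 6 months". Just before it, Section J names calories as the comparison for Specific Aim 2.

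Section I.1 lists height, weight and BMI under physical examination, next to the history items. It gives no time point and no method of measurement.

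Section H.3 says "Section N details the schedule of measurements", which makes Table 1 in Section N the governing schedule. Section H.3 allows telephone or mail for the 1-, 3- and 6-month contacts. Section I is narrower: "The assessments at 1-month, 3-months, and 6-months will take place by mail and will not require a visit to the clinical site". The only in-person contact scheduled after discharge is the clinic visit, for which Section I allows a "one-week window on each side of the postoperative visit planned at 2-3 weeks".

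Section E.2 excludes patients who are "Less than 18 years of age".

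**The concern.** The analysis section asks for a measurement that no other part of the plan arranges to collect. Both analysis times coincide with contacts at which nobody at the site sees the patient, and the schedule lists no weight at those contacts or at any other.

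Weight matters here because the Aim 1 hypothesis in Section A is that supplementation works by prolonging adequate nutrition. Weight is the only measure of body status that the plan compares between groups. If it is missing, a null quality-of-life result would be hard to interpret: the reader could not tell whether better nutrition failed to help or whether nutrition did not improve. Calories could in principle answer part of that question, but they have no collection row either.

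**Working it through.** No formula or stated figure is at issue. The check sets the analysis against the data collection.

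1. **Required by Section J:** weight and height in both groups at 30 days and at 6 months.

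2. **Scheduled in Table 1:** nine rows, namely eligibility, consent, demographics, Charlson index, quality of life, randomization, adverse events, length of stay and costs. The 1-month column holds quality of life and adverse events. The 6-month column holds those two and costs. Scheduled weights: 0 at 1 month, 0 at 6 months, 0 at any other time, screening included.

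3. **Section I.1:** weight is listed, but its position beside history items only suggests baseline. The one item there labelled as baseline is the Charlson index. Section H says the demographics and history forms are given once, before surgery. Even if weight sits on such a form, that supplies no follow-up value.

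4. **Contact mode:** the 1- and 6-month contacts are remote. Neither Section H.3 nor Section I mentions self-reported weight, home scales or weights taken from the chart.

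5. **Could the clinic visit stand in for day 30?** Let d be the day of discharge after surgery, and count the visit from discharge as Section H.3 does. With the 2-3 week timing and one-week window of Section I:
   - earliest day = d + 14 − 7 = d + 7
   - latest day = d + 21 + 7 = d + 28

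   The documents give no discharge day. Assuming d = 8, the visit falls between day 15 and day 36. Assuming d = 14, it falls between day 21 and day 42. So some visits could fall near day 30, but no weight is scheduled at that visit. No in-person contact is scheduled near 6 months.

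6. **Does the clinic visit follow the feeding period?** Taking the month as 30 days, it ends at about day 30 if counted from surgery, or at about day 8 + 30 = 38 if counted from randomization on day 8. A visit between day 15 and day 36 can precede either end, so a clinic weight alone would not describe the completed intervention.

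7. **Height:** everyone enrolled is an adult, so height at follow-up cannot reflect a month of tube feeding.

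8. **Calories:** Section J plans the comparison, but gives no time point, and Table 1 has no row for it.

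**The case against.** The strongest counter-argument is that the data could still exist. Patients can report a weight by mail or telephone, and the clinic visit may fall near day 30. Section H also draws on long-term data from the companion study, although it lists them for complications. A reader might infer that the comparison cannot be produced at all. The documents do not support that: they leave source, method and timing unspecified, which is a narrower defect.

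Table 1 is also not exhaustive. Medical history, readmission and jejunostomy-tube complications are to be collected and have no rows of their own. A missing row is therefore not proof that sites would record no weight. However, Section H.3 names Section N as the schedule, and no other section gives weight a time point.

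Two other inferences fail. A reader might take weight to be the only nutrition comparison in the plan, but Section J also names calories. A reader might expect that any weights found would come mainly from patients with problems. That is conceivable, but nothing in the documents establishes it.

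Finally, weight is absent from the aims in Section A and from the outcomes in Sections D, H.1 and H.2. That limits its importance, and it also means that no other section supplies the missing definition. The wording on height may be loose shorthand for body measurements, so that part is minor.

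**Conclusion.** The point holds as a mismatch between analysis and data collection. Section J names a weight comparison at two times, and the schedule provides zero weights at those times and zero at baseline. This rests on reading Table 1 as the governing schedule, and on the documents being silent about weights in the companion study. If that study does record weight near 1 and 6 months, the remedy may be no more than a cross-reference.

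The primary outcomes are unaffected. The gap should still be closed before enrolment, because a weight not recorded at the time may be unrecoverable. Height contributes nothing as an outcome, and calories share the gap.

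**What to change.** Add a weight row to Table 1 with method and windows:
- screening: measured;
- 2-week clinic visit: measured, and supportive only, because it can precede the end of the feeding month;
- 1 and 6 months: a current-weight item on the existing mail or telephone contact, labelled self-reported.

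In Section J, replace the height-and-weight sentence with a between-group comparison, at 1 and 6 months, of percent weight change from the pre-operative weight (or of weight adjusted for it). Delete height as an outcome. If companion-study weights are to be used, say so and give their timing. Calories need a similar decision: a collection row and time point, or removal from Section J.

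The cost is one entry at each of two existing visits and one item at each of two existing remote contacts. For co-enrolled patients, Section H has quality of life collected under the companion protocol, so the item may need a separate sheet or a change there. Self-reported weight is less precise and comes from unblinded patients, so it should be read beside the measured clinic weight. Change from a pre-operative value also includes loss before randomization. That loss should balance between groups on average, and it mainly costs precision.
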